#### **Sensitivity analyses:**

In the primary outcome analysis, we will implement LASSO using the R package `glm` in models that contain only the fixed covariates. After using LASSO to select a best set of fixed covariates, we will potentially add one or more of the three time dependent covariates to that list using stepwise procedures.

The primary analysis, in subjects who are lost to follow-up, will include only the available data until the time they lost to follow-up. However, we would like to be cautious in interpreting these results because a potential non-random dropout could bias the results. Hence, we will perform sensitivity analyses using multiple imputation.

Additional pre-specified statistical analysis will examine subset differences between children who were intubated during the acute RSV bronchiolitis and children who were not intubated in order to better interpret the results of the primary analysis based on the entire data. This will be performed by the following steps:

1. We will examine potential differences in baseline covariates between children who were and were not intubated. If this analysis will yield at least some suggestion of a between-group difference ( $p < 0.1$ ), the presence/absence of intubation will be included as a covariate in the model that will be used for the primary outcome analysis.
2. We will explore potential interaction between intubation and study treatment assignment although power to detect such differences may be low (no preliminary data is available to project the expected power).

3. We will repeat steps #1 and #2 for examining the effect of any mechanical ventilation (intubation, CPAP, BiPAP).

Data regarding antibiotic use, systemic corticosteroids use, and the occurrence of upper respiratory infections will be also collected every two months. These data will be used to determine the rate of these events during each six months study interval, and these repeated measures data will be compared across groups using Generalized Estimating Equations (GEE).

Missing data in the mixed model repeated measures analyses will be handled in the following ways. First, subjects randomized during the second year may provide data only up to 30 months while subjects randomized during the third year may provide only up to 18 months of data. Since missing data caused by randomization in year two or three (as oppose to randomization at year one) will be completely at random, we will analyze the data we have without imputation and with no associated bias. Second, we will also assume random missingness in the situation where a subject may have missed a particular phone call but completed subsequent phone calls. Therefore, we will calculate values for a given six-month interval in which one of the two-month phone calls was missing by imputing for a particular missing two-month value the average of the values for the outcome measure in the relevant six-month interval that were not missing. For example, if the 4 month phone call was missing and if the two-month and 6 month call yielded 12 days and 24 days for a given variable, we will impute 18 days (the average of 12 and 24) for the missing four month value. In all of these mixed model analyses, the focus will be on the statistical contrasts that compare between-group differences in the change from baseline to 18 months, from baseline to 30 months, and from baseline to 42 months.

## **A.2. Microbiome outcomes:**

We will use the streamlined 16S analytical pipeline developed in The Genome Institute for the Human Microbiome Project to perform the microbiome analysis. Bacteria counts will be rarified to the same number across all the samples to minimize the bias potentially caused by read depth. To evaluate the effect of azithromycin treatment on the upper airway and gut microbiome, we will compare the bacterial community structure between azithromycin and placebo groups at each of the following 3 time points: randomization, week 2, and month 6, utilizing multivariate statistical testing that are widely used for 16S microbiome analysis. First, NMDS based on Bray-Curtis dissimilarity will be used to identify the microbial clustering patterns and assess the similarity between the two groups in a reduced dimensional space at two individual time points. Then, we will use PERMANOVA to test the significant differences of the overall bacterial community between the two groups. To correct for potential confounding factors, we will test individual variables in a PERMANOVA model. All the variables that show a trend towards an association with the treatment assignment ( $P < 0.15$ ) will be included in the model, as described previously. To identify the signature bacteria taxa that contribute to the difference between two compared groups, we will apply Metastats, a statistical approach developed in Human Microbiome Study for differential bacteria feature identification. P-values from multiple comparisons will be corrected by the false discovery rate (FDR) approach. Lastly, we will measure both alpha and beta diversity of the bacterial community in the two groups. Alpha diversity index such as Shannon diversity and richness to evaluate the complexity of the whole microbial community; Wilcox-sum-Rank testing will be used to test the difference of diversity between compared groups. Beta diversity represented by Bray-Curtis dissimilarity will be used to indicate the inter-subjects variation in the bacterial composition. All analysis will be performed by R (<http://www.r-project.org/>) and Bioconductor. The above analyses will allow us to characterize the microbial community at each individual sampling point, and to evaluate how it is affected by azithromycin treatment.

To examine the relationship between microbiome changes and the diagnosis of RW, we will apply a linear mixed model to bacteria of interest such as the bacteria that are significantly different between the two groups identified at individual time points, as we have previously performed. Microbiome data will be normalized to satisfy the assumption of normality by a logarithmic transformation. In the linear mixed model, transformed bacterial abundance will be modeled as the response, and the sample collection time points, treatment groups and RW outcome as fixed effects and patients as random effect. P-values from multiple comparisons will be corrected by the false discovery rate (FDR) approach.

Finally, we will perform a whole genome sequencing (WGS) on a subset of the bio-samples. Among all samples obtained at the end of study treatments, we will choose 50 samples with the strongest positive associations and 50 with the strongest negative associations with RW: these 100 samples will be selected for WGS sequencing. The library preparation, whole genome shotgun sequencing, and data processing will be performed as previously described in the Human Microbiome Project. We will characterize the microbial community structure at species the level, identify other microbial components such as viruses, and reconstruct the metabolic pathways of the bacterial community for each sample. Similar statistical strategies will be used for the WGS data as described in the 16S rRNA gene data analysis. We will be alert to any changes in data quality; if needed, we will modify methods or repeat samples to obtain rigorously validated results.

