#### *The APW-RSV proof-of-concept trial, microbiome outcomes*

[figure not shown]
We investigated whether azithromycin alters the airway microbial composition and whether these changes could be associated with RW by sequencing 16S rRNA genes in the nasal wash from 39 participants of the APW-RSV pilot trial. We compared the upper airway bacterial communities at randomization and at the end of treatment (2 weeks later). As illustrated by Nonmetric Multi-dimensional Scaling (NMDS) based on the Bray-Curtis dissimilarity (**Figure 4 left**) and confirmed by permutational multivariate ANOVA (PERMANOVA), samples from azithromycin and placebo groups harbored similar bacterial communities at randomization. However, after two weeks of treatment, samples from the azithromycin group formed a distinct cluster (**Figure 4 right**), and the community structures of the 2 groups became significantly different. Longitudinal comparison revealed altered bacterial communities in both groups after two weeks of treatment. However, azithromycin and Placebo group’s microbiome changed with different patterns: decreased *Moraxella* ( $p=0.003$ ,  $q=0.03$  ( $q$ -value is an estimate of the False Discovery Rate)) in the azithromycin group, and increased *Corynebacterium* ( $p=0.008$ ,  $q=0.09$ ), *Dolosigranulum* ( $p=0.006$ ,  $q=0.07$ ), and decreased streptococcus in the placebo group ( $p=0.001$ ,  $q=0.004$ ). These preliminary findings suggest azithromycin has a significant impact on the composition of the upper airway microbiome during RSV bronchiolitis.

Differential feature analysis by Metastats, an analysis performs to identify the genera that contribute to the difference between two bacterial communities, showed that the *Moraxella* genus was the bacteria taxon that statistically distinguished ( $p=0.0002$ ,  $q=0.009$ ) the azithromycin and placebo groups at the end of study treatments (**Figure 5**).

Lower *Moraxella* abundance at the end of study treatments was significantly associated with lower odds of experiencing subsequent RW (OR=0.86; 95% CI 0.75-0.99,  $p=0.03$ ) suggesting that *Moraxella* may have a potential role in the development of post-RSV wheezing, and highlights the potential efficacy of the intervention to reduce the abundance of this taxon and probably other taxa, and hence to modify the clinical outcome of RW.

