## **III. HYPOTHESES TO BE TESTED BY THE APW-RSV II TRIAL**

### **A. PRIMARY HYPOTHESES**

In infants hospitalized with RSV bronchiolitis, the addition of azithromycin therapy (compared to placebo) to routine bronchiolitis care:

1. Reduces the likelihood of developing post-RSV RW ( $\geq 3$  episodes) measured over a follow-up period of 18-48 months.
2. Modifies the airway bacterial microbiome community structure, and these changes are related to the occurrence of post-RSV RW:
  - a. More specifically, based on our preliminary data we will evaluate if azithromycin therapy results in reduction of *Moraxella* abundance and whether lower *Moraxella* abundance is associated with reduced odds to develop RW.

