## 3. OTHER EXPLORATORY OUTCOME VARIABLES MEASURED DURING THE FOLLOW-UP PERIOD (18-48 MONTHS):

- a. Time to 4th wheezing episode.
- b. Annualized number of days with wheezing.
- c. Annualized number of days with parental absence from work due to child's respiratory symptoms.
- d. Annualized number of days with child absence from day care.
- e. Annualized number of days with nights with awakening due to respiratory symptoms.
- f. Rates of ED and urgent care visits.
- g. Rates of hospitalizations for respiratory symptoms.
- h. Rates of upper respiratory infections.
- i. Proportion of children prescribed asthma controllers medications (ICS, LTRA).
- j. Cumulative number of wheezing episodes.
- k. Proportion of children with at least one positive specific IgE (SIgE) to inhalant allergen at V3 and at the end of study visit (see Section O for details on the specifics allergy testing).
- l. Total IgE level and eosinophil count measured at the last study visit.
- m. Determine if demographic (sex, age, race), baseline asthma/allergy phenotypic characteristics (Personal/family atopic history, second hand smoking, pet exposure), RSV serotype (A vs. B), peripheral eosinophil count, and the presence of co-infection with other respiratory viruses during the RSV bronchiolitis (e.g. rhinovirus) and/or bacteria are predictors of response to azithromycin therapy.
- n. Changes in upper airway microbiome community structure following study treatments.
- o. Upper airway microbiome community structure measured 6 months following randomization.
- p. Based on our preliminary data we will specifically evaluate if azithromycin therapy results in reduction of *Moraxella* abundance and whether lower *Moraxella* abundance is associated with reduced odds to develop RW.
- q. Compositions of the viral and/or the fungal components of the upper airway microbiome, and the composition of the stool microbiome (these will be explored based on availability of additional funding).

Secondary clinical outcomes will be assessed by clinic visits and phone call interviews as described for the primary outcome. These will be measured as we previously described.

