### **B.2. Microbiome outcomes:**

We will utilize the whole study population (n=200) for this aim. This sample size provides 90% power to detect the difference for a given taxa between two groups, with effect size (5%) and standard deviation (SD1=2 and SD2=10) and alpha=0.05. However, 141 patients will be sufficient to provide 80% power to detect the same effect size. All sample size calculations assume 10% sample failed rate, which may be from different stages of the experiments,

**Figure 3.** Anticipated effect size of the intervention: proportion of patients who will not develop recurrent wheeze in the 2 treatment groups

such as patient drop out, sample preparation and sequencing failure (the combined failure rate related to the last 2 reasons in our APW-RSV trial was less than 4%). These power calculations were performed based on the assumption that we will observe half of the effect size and standard deviation detected in our preliminary data, in which *Moraxella* decreased significantly after azithromycin treatment. We used a decreased effect size to infer the sample size as *Moraxella* was a relatively high abundance taxon in the data and was affected by the intervention in our preliminary studies. In this proposal, we are also interested in comprehensive detection of the difference of relatively rare taxa in those two groups. We will be more confident to classify relatively rarely taxa in the Miseq deep sequencing platform (we anticipate 4x more reads/sample) than with the Roche 454 sequencing platform, in which our preliminary data was generated.

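### Moraxella is named in advance in hypothesis 2a, but VII.A.2 gives it no baseline-adjusted single-taxon test of treatment outside the FDR family

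*Combined protocol and SAP*

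**What the plan says.** **The hypothesis.** Section III.A, item 2a, sits under the primary hypotheses and says "we will evaluate if azithromycin therapy results in reduction of *Moraxella* abundance", and whether lower abundance goes with lower odds of RW. Section V.F.3, item p, lists the same question among the exploratory outcomes: "Based on our preliminary data we will specifically evaluate if azithromycin therapy results in reduction of *Moraxella* abundance".

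**The sizing.** Section VII.B.2 starts from "We will utilize the whole study population (n=200) for this aim". It claims 90% power for one taxon with a difference of 5%, SDs of 2 and 10, alpha 0.05 and 10% sample failure, and 80% power with 141 patients. No multiplicity adjustment is included. The inputs are described as half the pilot effect and SD, the pilot result being the fall in Moraxella. The same section adds that "we are also interested in comprehensive detection of the difference of relatively rare taxa in those two groups".

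**The analysis.** Section VII.A.2 does not mention Moraxella. It compares arms separately at randomization, week 2 and month 6, uses Metastats to find the taxa that differ, and states "P-values from multiple comparisons will be corrected by the false discovery rate (FDR) approach". For the link with RW, "we will apply a linear mixed model to bacteria of interest such as the bacteria that are significantly different between the two groups". That model has log abundance as response, time point, treatment and RW as fixed effects, and patient as random effect. It too is FDR-corrected. Neither the FDR level nor the number of taxa is given.

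**Baseline adjustment elsewhere.** The secondary-outcomes part of VII.A prescribes analysis of covariance on the baseline value for biological measures, with IL-8 as the example. VII.A.2 neither repeats this nor refers to it.

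**The concern.** A single taxon fixed before the data are seen need not share an error budget with every other taxon sequenced. Under VII.A.2 it does, so a real Moraxella effect could be reported as non-significant because many exploratory taxa were tested beside it. The family may also grow, since VII.B.2 aims at rarer taxa with deeper sequencing.

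The mixed model does not fill the gap. Without a treatment-by-time term, its treatment coefficient averages over whatever time points enter. If randomization samples are included, where no drug effect can exist, the week-2 effect is diluted. With randomization and week 2 only, and equal numbers at each, the coefficient targets (0 + d)/2, half the week-2 effect d. The model also treats abundance as the response, whereas 2a asks about the odds of RW.

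Power is not the only issue. A hypothesis listed as primary has no stated model, time point or threshold, so these remain open to choice after unblinding.

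**Working it through.** **Inputs from VII.B.2:** difference 5; SDs 2 and 10; alpha 0.05 (two-sided assumed); 10% failure, so 200 gives 180 analysable, 90 per arm under 1:1 allocation.

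**Step 1: reproduce the plan's figures.** Normal approximation, n per arm = 2 × SD² × (z_alpha + z_power)² / 5², total divided by 0.9.
- Printed SDs: SD² = (2² + 10²)/2 = 52, SD = 7.21. For 80%: 2 × 52 × 7.85/25 = 32.7, so 33 per arm, 66/0.9 = 74 in total. For 90%: 44 per arm, 98 in total. These are not 141 and 200.
- SD 10 in both arms: 63 per arm, 140 in total for 80% (stated 141); 85 per arm, 189 in total for 90%, and 200 gives 91.8%.

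The stated totals fit SD 10 in both arms, not the printed pair. That is a separate issue, but it means both cases must be carried forward.

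**Step 2: number of taxa.** The documents give none. In II.B.2 the pilot reports that the Moraxella "genus was the bacteria taxon that statistically distinguished" the two arms at the end of treatment, with p = 0.0002 and q = 0.009. The ratio 0.009/0.0002 = 45 suggests about 45 taxa if Moraxella ranked first under Benjamini-Hochberg (assumption). Ratios for the within-arm comparisons are lower: 0.03/0.003 = 10, 0.09/0.008 = 11, 0.07/0.006 = 12 and 0.004/0.001 = 4. Range used: 10 to 100.

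**Step 3: power under FDR.** If Moraxella is the only true signal, a 5% FDR (assumed) over m taxa acts approximately as a threshold of 0.05/m. Power = Φ(5/(SD × √(2/90)) − z). The expected z is 5/1.075 = 4.65 on the printed SDs and 5/1.491 = 3.35 with SD 10/10. For m = 45 the threshold is 0.0011, z = 3.26. The last column starts from exactly 90% power, expected z = 1.96 + 1.28 = 3.24.

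| Taxa m | SD 2/10 | SD 10/10 | From stated 90% |
|---|---|---|---|
| 1 (no correction) | 99.6% | 91.8% | 90% |
| 10 | 96.7% | 70.8% | 67% |
| 20 | 94.8% | 63.0% | 59% |
| 45 | 91.8% | 53.7% | 49% |
| 100 | 87.9% | 45.0% | 41% |

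A Benjamini-Hochberg simulation (40,000 runs, independent taxa) agrees: 54.7% for SD 10/10, m = 45. With 5 non-null taxa of equal strength among the 45, power is 69.0%; with 10 it is 77.1%. On the printed SDs, 5 of 45 gives 97.0%.

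**Step 4: baseline adjustment.** This multiplies the SD by √(1 − r²). With r = 0.5 (assumed; none is given) and SD 10/10, the SD becomes 8.66 and power at 0.05 rises from 91.8% to 97.2%, about 5 points.

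**Step 5: the RW half of 2a.** The pilot association was p = 0.03, with no q reported. With only two taxa in a 5% Benjamini-Hochberg family, the smaller p must be at or below 0.025 unless the other is also at or below 0.05. A result of pilot strength could fail because one other taxon was tested with it.

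**The case against.** Three stronger readings are tempting, and the documents do not support them.

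- *The screen is Moraxella's only route.* It is not. The mixed model is a second taxon-level analysis, and its wording gives screen hits as an example rather than a condition, so Moraxella may enter without passing the screen.
- *The baseline sample is ignored.* Time point is a fixed effect and patient a random effect, so randomization samples can enter. The analysis-of-covariance wording in VII.A, with IL-8 as an example, does not exclude abundance.
- *Power is roughly halved.* On the printed SDs it is not. Halving needs SD 10 in both arms or a start at the stated 90%, about 45 or more taxa, a 5% FDR level and no other true signal. At 10% FDR and 45 taxa, 90% falls to 57%.

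The pilot also offers reassurance: Moraxella passed FDR with 39 infants. Its z of 3.72 scaled to 180 analysable is 3.72 × √(180/39) = 8.0. Halved for pilot optimism to 4.0, it still gives 77% power at the 45-taxon threshold and 98% uncorrected.

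Finally, the primary microbiome outcome in V.F.1 is community structure, for which PERMANOVA needs no taxon-level correction. V.F.3 item p calls the Moraxella question exploratory, and FDR is defensible for an exploratory item. Omitting baseline in a randomized comparison loses precision but causes no bias.

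All of this limits the size of the problem. It does not supply the missing test: permission to include Moraxella is not a pre-specified contrast, and item 2a still stands among the primary hypotheses.

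**Conclusion.** The point holds as a gap in specification with a power cost. Section III.A names Moraxella and VII.B.2 sizes for one taxon at alpha 0.05, but VII.A.2 contains no single-taxon, baseline-adjusted test of treatment outside the FDR family.

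With a 5% FDR level and Moraxella as the only signal, the cost is about 5 to 12 points on the printed SDs (99.6% to 94.8-87.9% for 20 to 100 taxa). It approaches half only at the upper end: 91.8% to 53.7% with SD 10/10 and 45 taxa, or 90% to about 49% from the stated power. With 5 non-null taxa of 45, the SD 10/10 figure is about 69%. Nearly all of the loss comes from FDR; leaving out baseline costs about 5 points (r = 0.5, SD 10/10).

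The FDR level, number of taxa, independence between taxa, sidedness and r are assumptions. A missed Moraxella effect is a risk, not a forecast.

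**What to change.** In VII.A.2, before unblinding:

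1. Pre-specify one test of week-2 log Moraxella abundance by arm, adjusted for log abundance at randomization (the analysis of covariance already used for IL-8), two-sided 0.05, outside the FDR family.
2. Pre-specify one test of the association between week-2 Moraxella and RW, with its model and threshold stated, run whatever the screen shows.
3. Keep the FDR correction for all other taxa.
4. Reconcile III.A item 2a (primary) with V.F.3 item p (exploratory), so that the report gives the Moraxella result one status.

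The cost is a few sentences of SAP text. The randomization and week-2 samples are already in the visit schedule, and the exploratory taxa lose nothing.

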## F. PRIMARY OUTCOME MEASURES AND RATIONALE

### F.1. Primary outcomes:

1. Clinical trial primary outcome: The time until the occurrence of a third episode of post-RSV wheezing measured over a follow up duration of 18-48 months, quantified by a Cox proportional hazards regression model, and compared between the groups.

*Time frame for primary outcome assessment:* For the purpose of this study, wheezing detected during the initial RSV bronchiolitis will not be included in the count of post-RSV wheezing. The time frame for measurement of post-RSV wheezing (and other long-term outcomes) starts at the end of the treatment period (2 weeks after randomization) and ends at end of the follow-up period. Therefore, a wheezing episode that occurs at the first 2 weeks of the study, does not “count” toward the outcome of RW.

2. Microbiome study outcome: Upper airway microbiome community structure measured at the end of study treatments, and its relationship with the occurrence of post-RSV RW ( $\geq 3$  episodes).

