### Rationale for using survival analysis methodology for the primary outcome assessment:

In order to maximize the duration of follow-up in this trial which will recruit subjects over 3 consecutive RSV seasons, participants will have variable follow up durations based upon the year in which each participant will be recruited: the first season's recruits will be followed for up to 48 months, the second season will be followed up to 36 months, and the third season will be followed for at least 18 months. Maximizing the duration during which we will monitor the effect of the intervention will result in a higher likelihood of detecting the difference in outcomes between treatment groups. **Based on this study design with variable duration of follow-up, survival analysis methodology is most appropriate.**

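### The only model linking the microbiome to recurrent wheeze (RW) pools RW over the sampled time points and ignores follow-up length, so it does not test the stated end-of-treatment question.

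*Combined protocol and SAP*

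**What the plan says.** Sections II.F.1 and V.F.1 list as a primary outcome "Upper airway microbiome community structure measured at the end of study treatments, and its relationship with the occurrence of post-RSV RW". Primary hypothesis 2 (III.A) is worded in terms of change: "Modifies the airway bacterial microbiome community structure, and these changes are related to the occurrence of post-RSV RW".

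Section VII.A.2 first compares the treatment arms "at each of the following 3 time points: randomization, week 2, and month 6". It then introduces a linear mixed model, fitted to taxa of interest, with the purpose "To examine the relationship between microbiome changes and the diagnosis of RW". In that model "transformed bacterial abundance will be modeled as the response, and the sample collection time points, treatment groups and RW outcome as fixed effects", and patient is a random effect. No other model in VII.A.2 relates the microbiome to RW.

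On follow-up, the rationale for survival analysis in VII.A says that "the first season's recruits will be followed for up to 48 months, the second season will be followed up to 36 months" and that "the third season will be followed for at least 18 months". It concludes: "Based on this study design with variable duration of follow-up, survival analysis methodology is most appropriate". That reasoning is given for the clinical outcome and is not carried into VII.A.2.

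**The concern.** A main effect of RW in a repeated-measures model answers this question: averaged over the samples, do children with RW differ in abundance from children without? The protocol asks about the week-2 sample, or in III.A about change. The randomization sample precedes treatment. The month-6 sample can follow the third wheeze, so for some children it is not a predictor at all.

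The RW term is also a bare outcome. A child from season 3 with 18 months of follow-up and a child from season 1 with 48 months are both entered as no RW if no third episode was seen.

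At stake is whether a listed primary outcome has a pre-specified test. Under the present text the reported coefficient could be null when a week-2 association exists, or positive because of differences already present before treatment.

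**Working it through.** **1. Does any planned analysis test week 2 against RW?**
- The per-time-point tests in VII.A.2 (NMDS, PERMANOVA, Metastats, diversity) are set up to compare azithromycin with placebo, not RW groups.
- The mixed model has RW as a main effect only.
- The pilot related end-of-treatment *Moraxella* to the odds of later RW (OR 0.86, II.B.2), and V.F.3(p) repeats that question as odds. VII.A.2 names no model that yields an odds or hazard ratio for RW.
- The only microbiome power figure (VII.B.2) is for a difference in one taxon between two groups, justified by the pilot's treatment effect. None is given for the RW model.

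**2. Reproducing the plan's RW curves (VII.B.1).** Placebo monthly hazard: 2% in months 1-3, rising linearly to 5% at month 12, falling linearly to 3% at month 24, 2% in year 3, 1% in year 4. Azithromycin: hazard ratio 0.5 to month 24, then 1. The plan states a ratio of at least 2 (placebo to azithromycin) for 18 months and 1 in years 3-4, so months 19-24 are an assumption. Cumulative risk = 1 − Π(1 − h).
- 48 months: 71.1% placebo (plan 71.6%) and 54.9% azithromycin (plan 55.1%). Reproduced.

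**3. Timing and label, from those curves**

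| | Placebo | Azithromycin |
|---|---|---|
| RW by month 6 | 13% | 7% |
| RW by 18 months | 48.74% | 28.16% |
| RW by 48 months | 71.06% | 54.94% |
| Eventual RW labelled no at 18 months | 1 − 48.74/71.06 = 31% | 1 − 28.16/54.94 = 49% |
| Same, at 20 months | 26% | 44% |

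**4. What pooling does.** For balanced data with a random intercept, the RW main effect equals the regression of each child's three-sample mean on arm and RW. With between-sample correlation ρ, that mean has variance (1 + 2ρ)/3 in units of one sample's variance. The ratio of the pooled z-statistic to a week-2 z-statistic is then:
- difference at week 2 only: (1/3)/√((1 + 2ρ)/3) = 1/√(3(1 + 2ρ)) = 0.53, 0.46, 0.41 at ρ = 0.1, 0.3, 0.5. A week-2 test with 90% power falls to 40%, 31%, 26%.
- same difference at all three samples: √(3/(1 + 2ρ)) = 1.58, 1.37, 1.22, a gain.

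**5. Simulated power.** 180 usable children (200 less the 10% sample failure in VII.B.2) and the hazards above. The assumptions are log hazard ratio 0.25 per SD and ρ from 0.2 to 0.6.

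| Analysis | Week-2 abundance drives RW | Stable trait drives RW |
|---|---|---|
| Planned pooled model | 32-48% | 30-52% |
| Cox on week 2, adjusted for arm | 67-71% | 19-43% |
| Cox on week 2, adjusted for arm and baseline abundance | 49-62% | 16-19% |

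A separate run at hazard ratio 1.35 per SD and ρ = 0.1, 0.3, 0.5, with week-2 abundance driving RW, splits the loss. Pooled model: 37%, 50%, 58%. Week 2 with the same yes/no label: 75%, 76%, 75%. Cox: 81% throughout. Most of the difference comes from isolating week 2. Across the settings tried, the label alone costs about 4-7 points.

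**The case against.** The strongest case for the plan has four parts.

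- **The text may be incomplete rather than wrong.** It does not say that all three samples enter this model, it does not exclude an interaction, and it refers to a method the group has used before. That is fair. But a primary outcome needs its test named, and the terms that are listed give a pooled coefficient.
- **Repeated samples suit a question about change,** which III.A and the model's own purpose statement both raise. This also stands as far as it goes. However, a main effect of RW describes average level, not change; change would need an RW-by-time term.
- **Averaging can help.** A reader might infer that the planned model simply loses power. The documents do not support that. If RW tracks a stable feature of the child's microbiome, pooling is the more powerful analysis, and a week-2 Cox model that also adjusts for baseline abundance does much worse. Even when week-2 abundance drives RW, the baseline-adjusted model's advantage shrinks as the correlation rises.
- **The label is a lesser problem.** A reader might infer from the 31% and 49% figures that the unequal follow-up biases the treatment comparison. It does not follow: season of enrolment is unrelated to randomized arm, so the label mainly dilutes the RW association.

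It is also fair that a taxon-by-taxon model, however timed, does not by itself address community structure.

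**Conclusion.** The mismatch stands and needs no simulation: as written, the only microbiome-to-RW model tests neither the end-of-treatment association (II.F.1, V.F.1) nor the change named in III.A and VII.A.2. It also treats RW as free of time and censoring, in a design for which the plan itself calls for survival methods.

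The size of the consequence is conditional. Against a week-2 Cox model adjusted for arm, the pooled model is clearly weaker if week-2 abundance itself relates to RW (about 32-48% against 67-71%). It is stronger if a stable trait does (30-52% against 19-43%). These figures rest on an assumed log hazard ratio of 0.25 per SD and correlations of 0.2 to 0.6, neither of which the documents give. The month-6 figures (13% and 7%) and the label figures rest on the plan's own hazards, with the azithromycin ratio of 0.5 extended to month 24. The label is the smaller part of the problem.

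The plan should be changed, because this is a listed primary outcome and the repair is inexpensive.

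**What to change.** In VII.A.2, pre-specify one primary week-2 test against RW. Either option is acceptable:
1. A Cox model for time to third wheeze, counted from the end of treatment, with week-2 abundance as predictor (*Moraxella* first, other taxa FDR-corrected), adjusted for arm and the antibiotic-use stratum.
2. The existing mixed model with an RW-by-time term, a named week-2 contrast, and an explicit way of accounting for follow-up length.

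In addition:
- Add a community-level week-2 test against RW, for example PERMANOVA, because the stated outcome is community structure.
- Adjust for baseline abundance only in a separate analysis labelled as change.
- Keep the pooled mixed model as supportive, stating which samples enter it.
- Give power for the chosen test over a stated range of effect sizes and, where it matters, between-sample correlations.

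The cost is SAP wording; the samples and follow-up are already scheduled. The one statistical downside is lower power if the association turns out to be a stable trait, which the retained pooled model would help to show.
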